b) Number of Subjects: 121. Sample size and Power Analysis: The proposed study will recruit 37 subjects for each of the ST, PR and DC1 treatment conditions, and 10 subjects for the CD2 group. The study has 93% power to detect a 50% difference in relapse rate between group 2 and group 3 over the 2-week assessment period, even account for 10% dropout rate based on a two-sided $\alpha = 0.05$ using the method of Lakatos, E. (35). We selected a 50% relapse rate difference for the power calculation based on our prior experience. For the primary continuous symptom measure blood pressure, we have 80% power to detect about a medium effect size 0.56 based on a longitudinal study design with 7 assessment points, a conservative estimate of within-subject correlation 0.5, and a two-sided type I $\alpha=0.05$ using the method of Tu et al. (36). Note that although blood pressure is assessed twice daily in Experiment 1, we conservatively set the number of assessments at 7 to improve the robustness of the power estimates. Thus, the proposed sample size not only has sufficient power to detect a clinically meaningful difference in relapse rates, but also to find meaningful change patterns for blood pressure over the treatment course.

c) Sex of subjects: The male to female ratio will follow the distribution of hypertension in the Rochester area community. Pregnant or nursing females will be excluded due to the nature of the intervention (carvedilol is Category C). Females of child bearing potential will be required to use 2 birth control methods during the study in order to participate.

d) Age of Subjects: 18 to 80 years of age. Carvedilol is not intended for use in children.

e) Racial and Ethnic Origin: No restrictions. It will follow the distribution of patients seen in the Rochester area.

f) Vulnerable Subjects: None will be enrolled.

III. METHODS AND PROCEDURES

a) **Study Design.** Randomized, single blind.

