If, as anticipated, there are a sufficient number of patients from Experiment 1 who show no evidence of relapse within the 15-day experimental period, we can proceed to Experiment 2. The remaining patients from the Standard Therapy and Partial Reinforcement Groups (and, perhaps, the Dose Control Group-1) would be divided into two subgroups. For one subgroup, all medication would be discontinued for a period of 2-4 wk; for the other subgroup, active drug would be discontinued but the patients would continue to receive the distinctive capsules containing inert substance. It is predicted that: (a) patients reexposed to the CS will be less likely to relapse or show a slower rate of relapse than patients in groups that are not reexposed to the CS; and (b) patients in the Partial Reinforcement Group will be more resistant to extinction (slower to relapse) than patients remaining from Dose Control Group-1 who were treated with the same cumulative amount of drug and may even be indistinguishable from the Standard Therapy Group that had received three times more drug. An alternative strategy, of course, would be to enlist a new population.

c) Statistical Analysis: Data analyses are described separately for each of the specific hypotheses. All statistical tests will be two-sided with $p \leq .05$. The principal analyses focus on the difference over 2-weeks between PR and two dose control groups (DC-1 and DC-2) in Experiment 1. The main independent variable is time to relapse as well as symptom reduction (blood pressure). These two outcomes will also be examined in Experiment 2 to see if they differ between the two groups (placebo and no-treatment groups). Because power for the comparisons in the second experiment may be undercut by high relapse rates in the first experiment, this second set of analyses is exploratory.

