The Cox proportional regression model will be used to examine the time to relapse outcome, while mixed-effects (MM) model will be used to compare differences in symptom reductions over time across the treatment groups. The MM approach employed for longitudinal data analysis provides valid inference under the missing at random assumption (MAR), provided that the parametric distribution assumptions are met. The MAR model is quite general, accommodating almost all missing data mechanism that may arise in practical studies (37,38). However, in the presence of missing data, estimates in both cases may be biased if the data fails to follow the assumed statistical distributions, even with the use of the sandwich variance estimates (39). In cases where distribution assumptions are seriously violated, for example, if discrepancies between the MM and WGEE for fixed-effects show very different results, we will use clustered bootstrap methods for inference (40).

Experiment 1

AIM 1: a) PR will be more effective than DC-1 and DC-2 in reducing relapse rates. PR will have similar effectiveness to ST in reducing relapse rates.

Survival analysis will be conducted using Cox proportional hazards model. We will include dummy variables for the four treatment groups in addition to the covariates found to significantly differentiate the groups at baseline. Appropriate linear contrasts will be constructed to compare PR vs. each of the dose control groups, if a significant group difference is found.

Note that to formally confirm the equivalence between PR and ST, we must use non-inferiority tests. However, since the acceptable margin of tolerable difference is difficult to define due to the lack of insufficient literature on this topic, we will not conduct such a formal analysis. The effect size will provide similar indications of treatment difference.

b) PR will have higher (similar) symptom reductions than DC-1 and DC-2 (ST).

Longitudinal methods will be applied to compare the outcomes of pruritus and biologic measures across the four groups as well as the appropriate pairwise comparisons. We will dummy code the treatment conditions, include time and time by treatment interaction in addition to the covariates found to differentiate

the four groups at baseline. The hypothesis will be supported if a significant time by treatment interaction is found. Appropriate linear contrasts will be performed to compare PR vs. DC-1, DC-2 and ST.

Experiment 2

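### Similarity of partial reinforcement (PR) to standard therapy (ST) is part of Aim 1, but an effect size with no interval or criterion stands in for the test the plan says is needed

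*Combined protocol and SAP*

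**What the plan says.** In the combined protocol and SAP, section III.c, Experiment 1, Aim 1a couples superiority over the dose controls with a second prediction: "PR will have similar effectiveness to ST in reducing relapse rates". Aim 1b does the same for symptoms: "PR will have higher (similar) symptom reductions than DC-1 and DC-2 (ST".

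Under Aim 1a the plan acknowledges that equivalence of PR and ST would need a non-inferiority test. It declines to run one because a tolerable margin is hard to define, and closes with "The effect size will provide similar indications of treatment difference". It names no confidence interval, threshold or decision rule.

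The Cox contrasts listed under Aim 1a are PR against each dose control, and only after a significant overall group difference. PR against ST is not among them. Aim 1b does list a PR–ST contrast, but it takes a significant time-by-treatment interaction as support for the whole hypothesis, including the part about ST.

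The relapse power statement in II.b covers a different comparison: "The study has 93% power to detect a 50% difference in relapse rate between group 2 and group 3 over the 2-week assessment period". No power or precision is given for PR against ST.

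**The concern.** The last sentence of the Aim 1a note offers the effect size as an adequate stand-in for the test the plan has just called necessary. A hazard ratio near 1 from a small comparison can sit alongside a large true difference in either direction. Without an interval the reader cannot see that, and without a criterion nobody can say what result would count as similar.

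Aim 1b has a separate problem of logic. An interaction test across four groups looks for a difference. A significant result cannot show that two of those groups are alike.

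At stake is the comparison that bears most directly on the clinical promise in section I, which is a maintained effect on less drug. Under Table 1, PR receives an average of 6.25 mg daily against 25 mg for ST. A small or non-significant PR–ST difference could be read as evidence of similar effectiveness when the data do not establish it.

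**Working it through.** **Inputs**
- Arm size (II.b): "The proposed study will recruit 37 subjects for each of the ST, PR and DC1 treatment conditions".
- Dropout (II.b): "even account for 10% dropout rate". 37 × 0.9 = 33.3, so about 33 per arm and 66 in the PR–ST comparison.
- Error rate (III.c): "All statistical tests will be two-sided with" a 0.05 threshold.
- Relapse rate: none is given for any arm, so the rates below are assumptions. Experiment 2 expects a substantial share of PR and ST patients to remain without relapse, but gives no figure.

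**1. The plan's own figure.** The 93% concerns group 2 against group 3 (taken as PR and DC-1). Its basis is "We selected a 50% relapse rate difference for the power calculation based on our prior experience", with no base rate and no statement of whether the 50% is relative, absolute or a hazard ratio, so it cannot be reproduced uniquely. By Schoenfeld's formula, power = Φ(|ln HR|·√D/2 − 1.96), where D is the number of relapses:
- HR 0.5 gives at most 80% (D = 66) or 85% (D = 74), even if everyone relapses. Reaching 93% needs 99 events.
- A relative halving gives about 93% when DC-1 relapse is about 77% and PR about 39%.
- A 50-point absolute difference gives more than 96%.

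None of these readings provides a figure for PR against ST.

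**2. Precision for PR against ST.** With equal arms and equal relapse, SE(ln HR) = 2/√D. Around an *estimated* HR of 1.0, the 95% CI is exp(±1.96 × 2/√D).

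| Relapse in both arms (assumed) | D of 66 | 95% CI |
|---|---|---|
| 20% | 13.2 | 0.34–2.94 |
| 40% | 26.4 | 0.47–2.14 |
| 60% | 39.6 | 0.54–1.86 |
| 100% | 66 | 0.62–1.62 |

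If all 74 enrolled patients contribute, the first three rows become 0.36–2.77, 0.49–2.06 and 0.56–1.80. At the 39% PR rate back-solved in step 1, with 66 patients, the interval is 0.46–2.17.

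**3. Where the interval stops covering 0.5 and 2.** Setting 1.96 × 2/√D = ln 2 gives D = (3.92/0.6931)² ≈ 31.98. With 31 or fewer relapses the interval contains both values. From 32 it excludes them: 32/66 ≈ 48%, or 32/74 ≈ 43%.

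**4. If PR truly doubled the hazard** (33 per arm, PR relapse = 1 − (1 − ST relapse)²):
- ST 20%, PR 36%: D = 33 × 0.56 = 18.5, power 32%.
- ST 30%, PR 51%: D = 26.7, power 43%.
- ST 40%, PR 64%: D = 34.3, power 53%.

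In a Cox simulation of the first case (exponential times, 15 days, 4,000 runs), 73% of runs were non-significant and 16% gave an estimated HR of 1.25 or less. With a true HR of 1, the interval lay wholly within 0.5–2 in 0% of runs at 20–30% relapse, 5% at 50% and 17% at 60%.

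**5. What a formal test would need.** Events = 4(1.96 + z)²/(ln margin)², one-sided 0.025, true HR 1. With an illustrative margin of 2.0, 80% power (z = 0.84) needs 66 relapses and 90% power (z = 1.28) needs 88. A margin of 1.5 needs 191 and 256. The documents set no margin.

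**6. Aim 1b.** The interaction could be significant because PR and ST both differ from the dose controls, or because PR differs from ST. The stated criterion is met either way, so it says nothing about similarity to ST.

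**The case against.** Three stronger readings are tempting, and the documents do not support them.

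- *The plan will call PR similar to ST.* A reader might infer this, but Aim 1a is a prediction. The plan says openly that no formal test will be done, and it never says that a small or non-significant difference will be reported as similarity. It does not rule out a confidence interval, and a Cox fit supplies the standard error for one.
- *The trial cannot tell similarity from a doubling or halving at any relapse rate.* This fails from 32 relapses, and the 60% row above excludes both values. Experiment 1 also allows the experimental period to be extended, which could add events.
- *Blood-pressure precision is inadequate too.* This has not been shown. The detectable effect of 0.56 at 80% power in II.b implies a 95% half-width of about 0.39 SD (0.56 × 1.96/2.80), if it applies to equal PR and ST arms. Whether that is enough depends on a margin nobody has set.

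The comparison is also secondary. The account of Experiment 1 says that matching standard therapy is not critical for judging conditioning. III.c puts the principal analyses on PR against the dose controls, and none of the three numbered hypotheses in section I.a concerns PR against ST. Deleting every dropout is slightly pessimistic, since censored patients contribute until they leave.

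These points limit the weight of the concern but do not remove it. Similarity is still written into Aims 1a and 1b, and the sentence offering the effect size as a substitute is still wrong.

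**Conclusion.** The concern holds in a conditional form, as a wording defect in a secondary comparison that should be corrected. An effect size with no interval or criterion cannot support PR–ST similarity, Aim 1a names no PR–ST Cox contrast, and the Aim 1b criterion cannot show similarity. None of this depends on an assumed relapse rate.

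The size does. It assumes about 33 evaluable patients per arm, equal relapse in both arms and an estimated HR of exactly 1.0. On that basis the 95% CI contains both a halving and a doubling of the hazard below 32 combined relapses. The expectation that many PR and ST patients will not relapse makes such counts plausible, but the documents do not fix the number. Even if all 66 relapsed, the interval would be 0.62–1.62.

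**What to change.** 1. In Aim 1a, replace the effect-size sentence with wording such as: *PR versus ST will be estimated from the Cox model as a hazard ratio with a 95% confidence interval, whatever the result of the overall group test. No margin has been set, so similarity or non-inferiority will not be concluded from a small or non-significant difference.*
2. In Aim 1b, report the PR–ST contrast already planned, for blood pressure (the symptom outcome named at the start of III.c), with its 95% confidence interval. Limit the interaction criterion to the superiority part of the hypothesis.
3. Word the ST parts of Aims 1a and 1b as estimation.

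This needs no extra patients, visits or data. The price is giving up a secondary similarity claim. The principal comparisons with DC-1 and DC-2 do not change.

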The primary outcome measure will be the incidence and rate of “relapse,” defined as a blood pressure level that has risen to the baseline value (blood pressure value of the participant at the time of enrollment) for three consecutive days.

If, over the course of 15 days there is evidence of a gradual recurrence of symptoms, the experimental period can be extended. If there is no evidence of impending relapses, there are two options: (a) we can reduce the partial reinforcement schedule from 25% to 15%, for example, and adjust the dose of in the Dose Control Groups accordingly; or (b) proceed to a study of extinction effects (Experiment 2).

Timeline estimate. We propose a start-up period of 6 mo. (formulation of Consent Form, IRB approval of protocol, preparation of study personnel, data management procedures, preparation and placing of advertisements for study subjects, etc). Including an instructional session and testing of blood pressure measurements from the monitors provided to patients, patients enrolled in the study could be engaged for as many as 50-60 days. We calculate being able to process 40 patients/year. A final 6 mo. would be devoted to data processing and manuscript preparation and, thus, a total project period of 4 years.

Experiment 2. *Effects of CS exposure on the persistence of drug effects following the withdrawal of drug and the effects of partial schedules of pharmacotherapeutic reinforcement on resistance to extinction.*

Based on the time available and the outcome of Experiment 1, we may be able to gather additional preliminary data on the extinction of conditioned pharmacotherapeutic effects, adding evidence that results obtained in Experiment 1 are, in fact, the results of conditioning. We expect that patients in Dose Control Group-II from Experiment 1 will relapse within 2-3 days of the treatment imposed during the experimental period. A large percentage of Dose Control Group-I patients are also expected to relapse under a reduced dose of active drug during the experimental period. However, we expect that a significant percentage of patients in the Partial Reinforcement Group (as well as the Standard Therapy Group) would be available for further study of extinction effects.

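### Aim 1(b) claims a larger blood pressure reduction but is decided by the time-by-treatment interaction, which can miss an early, lasting PR benefit; the stated 80% power fits only gradual separation under linear time

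*Combined protocol and SAP*

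**What the plan says.** All from the combined protocol and SAP.

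- Section III c), Experiment 1, Aim 1(b), states the hypothesis as an amount: "PR will have higher (similar) symptom reductions than DC-1 and DC-2 (ST").
- The opening of section III c) does the same: "The principal analyses focus on the difference over 2-weeks between PR and two dose control groups (DC-1 and DC-2) in Experiment 1".
- The model under Aim 1(b): "We will dummy code the treatment conditions, include time and time by treatment interaction in addition to the covariates found to differentiate" the groups at baseline. The decision rule: "The hypothesis will be supported if a significant time by treatment interaction is found". Then: "Appropriate linear contrasts will be performed to compare PR vs. DC-1, DC-2 and ST". What these contrasts act on is not stated.
- Section II b), on power: "we have 80% power to detect about a medium effect size 0.56 based on a longitudinal study design with 7 assessment points", with within-subject correlation 0.5 and two-sided alpha 0.05. It does not say whether 0.56 is an average difference, an end-of-period difference or a slope.
- On timing, the Experiment 2 text says: "We expect that patients in Dose Control Group-II from Experiment 1 will relapse within 2-3 days of the treatment imposed during the experimental period". For DC-1 it expects many relapses during the experimental period but gives no day. The Experiment 1 text also allows for symptoms returning gradually over the 15 days.

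The Aim 1(b) sentence on longitudinal methods names pruritus and biologic measures. Sections II b) and III c) make clear that blood pressure is the continuous outcome.

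**The concern.** A time-by-treatment interaction asks whether the difference between groups changes over the modelled times. The hypothesis asks whether PR runs lower. The two questions can have different answers.

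Patients are randomised after responding to the same run-in treatment, and the amount of active drug is then reduced at once in three of the four groups. If PR and DC-1 separate in the first days and then stay apart, that is the therapeutic effect being sought. Yet most of the modelled period would show a constant difference, to which an interaction test responds weakly. Under the stated rule the trial could report Aim 1(b) as unsupported although PR held pressure below DC-1 for nearly the whole period. The power statement would give false comfort, because it does not say which course of the difference it assumes.

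**Working it through.** **Inputs.** From section II b): 37 per arm in PR and DC-1, 7 assessments, correlation 0.5, effect 0.56 SD, two-sided alpha 0.05. Assumptions: the same correlation between all pairs of readings; equally spaced assessments; normal approximation; and the 10% dropout, stated for the relapse calculation, applied here too, giving 37 × 0.9 = 33.3 per arm. Readings lost after relapse are not modelled.

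**1. Reproducing the 80%.** With 7 equally spaced times the centred indices are −3 to 3, with sum of squares 28. The first-to-last change on the fitted line (6 × slope) has variance 36 × (1 − 0.5)/28 = 0.643 per patient. The standard error of the group difference is √(2 × 0.643/33.3) = 0.1965. If 0.56 is the last-assessment difference, growing linearly from zero at the first, z = 0.56/0.1965 = 2.85 and power is 81%. A test of the average level has variance (1 + 6 × 0.5)/7 = 0.571, standard error √(2 × 0.571/33.3) = 0.185, z = 3.02 and power 86% (89% with 37 per arm). The stated figure therefore fits the slope test better.

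**2. Interaction power for other courses.** Each course of the difference is projected on linear time and divided by 0.1965. Example: the difference is complete by day 3 and the seven readings run from day 1 to day 15. The first difference is 0.56/3 = 0.187 and the rest are 0.56. Slope = (−3 × 0.187 + 3 × 0.56)/28 = 0.04; 6 × 0.04 = 0.24; z = 0.24/0.1965 = 1.22; power 23%.

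With time as a factor, the test is a 6-df chi-square with noncentrality (n/2) × Σ(d − mean d)²/(1 − 0.5), which is 33.3 × Σ(d − mean d)². In the same example this is 33.3 × 0.1195 = 3.98, giving 27%.

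| Full 0.56 SD reached | Day 1 start: linear | Day 1 start: factor | Day 0 included: linear | Day 0 included: factor |
|---|---|---|---|---|
| At once | 5% | 5% | 45% | 59% |
| Day 2 | 15% | 16% | 45% | 59% |
| Day 3 | 23% | 27% | 53% | 57% |
| Day 5 | 47% | 40% | 69% | 63% |
| Day 7 | 64% | 48% | 80% | 65% |
| Day 15, steady | 76% | 47% | 81% | 54% |

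A four-group interaction test gives much the same answer. With 33, 33, 33 and 9 patients, ST equal to PR, both dose controls 0.56 SD worse, and the full difference present from the second of seven time points, power is 45% (linear) or 59% (factor).

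**3. A level contrast.** Take the mean of four second-week readings, adjusted for b run-in readings. Variance per patient is 0.5 + 0.5/4 − 0.25/(0.5 + 0.5/b).

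- b = 1: 0.625 − 0.25 = 0.375; standard error √(2 × 0.375/33.3) = 0.150. Plateau by day 7 or sooner: 0.56/0.150 gives z = 3.73, power 96%. Steady growth: the mean difference over days 8–15 is 0.56 × 11.5/15 = 0.429; z = 2.86, power 82%.
- b = 3: variance 0.25, standard error 0.1225; power over 99% and 94%.
- No run-in covariate: variance 0.625, standard error 0.194; power 82% and 60%.

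**4. The interaction given the same run-in data.** With readings on days −2, −1 and 0 added as time points to the seven from day 1, interaction power is 92–93% for an immediate effect and 93–97% for a plateau by day 3.

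**The case against.** A reader might infer that the interaction test would usually miss a lasting PR benefit and that the 80% power claim is wrong. The documents do not support that much.

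- Expected means are equal at randomisation. If a pre-randomisation value is a time point, a lasting benefit is itself an interaction. The plan neither includes nor excludes such a value. With one day-0 reading, power for plateaus by day 2 to day 7 is 45–80%; with three it exceeds 90% in the early-effect cases checked. Much of the gap between the two tests therefore comes from using run-in data. Without it, the second-week contrast has only 60% under steady growth, below the interaction's 76–81%. This stands.
- The 80% can be reproduced. The fair criticism is that the plan does not say what 0.56 measures. This stands.
- The 2–3 day expectation concerns DC-2. It is not evidence that DC-1 separates from PR that early, and gradual return is also foreseen. This stands.
- Seven assessments is described as conservative. With 15 daily values, the first at randomisation, linear interaction power for a rise over three days then a plateau is 68–73% (33 to 37 per arm), still below 80%; for an immediate step it is 27–30%.
- The linear contrasts might address level. They might, but the plan does not say so, and support is tied to the interaction.
- Relapse is the primary outcome and Aim 1(a) would capture prevented relapse. That limits the consequence but does not repair Aim 1(b).

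**Conclusion.** The concern holds in a limited form. The only stated rule for supporting Aim 1(b) does not match a hypothesis about amount, and its power depends on choices the plan leaves open. For a lasting PR versus DC-1 difference of 0.56 SD complete by day 3 or sooner, linear interaction power is 5–23% if readings start at day 1 and 45–53% with one day-0 reading; with time as a factor it is 5–27% and 57–59%. The 80% holds for gradual separation under linear time (81% for steady growth with day 0 modelled). It does not hold for an early plateau with at most one pre-randomisation reading, nor for time as a factor under steady growth (47–54%). Since the plan foresees both rapid and gradual return, the rule should work under both. Like for like, with one pre-randomisation reading, the run-in-adjusted second-week contrast has 82–96% against 45–81% for the linear interaction. All figures rest on the assumptions listed above, in particular equal correlation between readings and no loss after relapse.

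**What to change.** Replace the support rule for Aim 1(b). Fit the mixed model to blood pressure with day as a factor, adjusted for mean pressure over the qualifying run-in days. Test the PR minus DC-1 difference in model-based mean pressure over a window fixed in advance, for example days 8–15. Keep the interaction as a description of the time course. Restate the power for this contrast and say what 0.56 measures. Treat PR minus DC-2 as supporting: with 10 patients in DC-2, power at 0.56 is only about 50–55% even for the average level. Aim 2(b) reuses the same methods, so its wording should follow.

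The cost is SAP wording. The run-in readings are already needed for the 10-point, five-day criterion.

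There is one small downside. The experimental phase is shorter for patients who relapse, and many DC-1 patients are expected to, so second-week readings will be thinnest in that arm. Continue home readings after relapse where available, or rely explicitly on the mixed model's missing-at-random assumption, and state power with that loss included.
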